**STUDY SCHEMA**

**STUDY SYNOPSIS**

Title	Phase Ib/II Trial of Interleukin-2 and PD-1 Checkpoint Inhibitor, Nivolumab In Metastatic Clear Cell Renal Cell Cancer
Phase	Phase Ib/II
Methodology	
Single arm, multi-site phase Ib/II clinical trial of standard doses of High Dose Interleukin-2 (HD IL2) (600,000 IU/kg/dose intravenously during two 5-day cycles 9 days apart) in IL-2 eligible clear cell metastatic RCC subjects in combination with Nivolumab.
 
Nivolumab will be administered intravenously at 480 mg/dose over 60 minutes every 28 days, starting 1 week to 3 weeks after the start date of the first cycle of IL2 and continued for up to 48 weeks total in the absence of disease progression by RECIST 1.1 criteria, unacceptable toxicity, withdrawal of consent or lack of clinical benefit as determined by the PI.
 
Nivolumab may be continued beyond 48 weeks off-study at the discretion of the investigator at his or her clinical judgment.
 
Initially 10 patients will be enrolled in the phase 1b portion of the study.
 
The first 3 patients will be treated with sequential (rather than interspersed) treatment. They will receive 2 cycles of HD-IL2 given in standard fashion (two 5-day cycles one week apart) followed by nivolumab starting the week after the second IL-2 cycle and continuing every 4 weeks as per standard nivolumab dosing.
 
We will perform a safety analysis after the first 3 patients are treated. If 2 out of 3 of the first patients suffer a grade 3 or 4 immune related toxicity, the study will stop. The 4th patient will not be enrolled until after the analysis of the 3 patient cohort is complete and submitted to the regulatory bodies.
 
If <2 patients suffer a grade 3 or 4 immune related toxicity, the study will enroll up to 7 more patients treated with Nivolumab administered intravenously at 480 mg/dose over 60 minutes every 28 days, starting 1 to 3 weeks after the start date of the first cycle of IL2. We will monitor these patients continuously for immune mediated dose limiting toxicities for 28 days from the first dose of nivolumab. If, at any time during accrual to the phase1 b portion, 6 patients or more have a grade 3 or 4 immune mediated event of interest (as described in section 5.2.1) we will pause the study and modify/discontinue the protocol in consultation with the site principal investigators and applicable regulatory authorities. If ≤ 5 of the 10 patients have a grade 3 or 4 immune mediated event of interest (as described in section 5.2.1), we will proceed to the phase II portion of the study. Please note: immune mediated events of interest do not include those that are known to occur during high dose IL-2 monotherapy and are reversible by holding IL2 dose(s) such as capillary leak syndrome.

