CR ranges from 7%-9%. Among the subjects who achieve CR, >80% remained disease free at last follow-up with a median survival over 10 years suggesting a durable response or a cure of mRCC. Alternate schedules and decreased doses of IL-2 have been tried without any improvement in outcome.

There are significant but manageable toxicities from HD IL-2 affecting multiple organ systems. These side effects include hypotension, cardiac arrhythmias, metabolic acidosis, fever, nausea and vomiting, dyspnea, edema, oliguria and renal failure, neurotoxicity, and dermatologic complications, and a mortality rate of less than 1% in recent trials.

SELECT Trial:

The Cytokine Working Group (CWG) designed and conducted the HD IL2 "Select" Trial. The primary objective of this prospective single-arm study was to evaluate prospectively whether an integrated selection model (ISM) based on clear-cell histology and carbonic anhydrase-9 (CA-9) IHC staining could identify a group of patients with advanced RCC and "good" predictive features who were significantly more likely to respond to HD IL2-based therapy than a historical, unselected patient population. During the course of this trial, retrospective analyses identified potential predictors of increased [e.g., programmed death-ligand 1 (PD-L1) expression, CA-9 gene SNP] and decreased (e.g., elevated pretreatment levels of fibronectin and VEGF) response to immunotherapy in patients with RCC.

[figure not shown]
One hundred and twenty eligible patients (of any histologic subtype of metastatic renal cell carcinoma type and no prior systemic therapy) were enrolled; 70% were Memorial Sloan Kettering Cancer Center (New York, NY) intermediate risk, 96% had clear cell RCC, and 99% had prior nephrectomy. The independently assessed ORR was 25% (30/120, 95% CI, 17.5%–33.7%,  $P = 0.0014$ ; 3 complete responses (2.5%), 27 partial responses (22.5%)) and was higher than a historical ORR. Thirteen patients (11%) remained progression free at 3 years and the median overall survival was 42.8 months. ORR was not statistically different by ISM classification ("good-risk" 23% vs. "poor-risk" 30%;  $P = 0.39$ ).

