### Dosing delays:

- **DURING IL-2 weeks**
  - Individual doses of IL-2 within each cycle may be skipped by the treating investigator at his or her discretion. Skipped doses will not be made up.
  
- **AFTER IL-2, BEFORE NIVOLUMAB**
  - All toxicities (with the exception of fatigue) attributed to IL-2 administration should have resolved or recovered to grade 1 or resolved or to baseline prior to starting nivolumab
  - Fatigue should have recovered to grade 2 or better
  - If toxicities have not improved to the levels listed above, nivolumab and the 2nd cycle of IL-2 should be held until toxicities improve to the above levels
  - If nivolumab or IL-2 is delayed >6 weeks as a result of a toxicity, the subject must be permanently discontinued from study therapy with the following exception:
    - If a steroid taper (to manage drug-related adverse events) is the reason for treatment delay of >6 weeks, and the subject's adverse events recover to grade 1 or better, continuation on study could be possible if approved by the principal investigator
  
- **AFTER NIVOLUMAB, PRIOR TO 2nd IL-2 CYCLE**
  - All immune mediated toxicities should have recovered to grade 1 or better prior to starting the second dose of IL-2 and subjects should be off systemic steroids or on a dose of ≤ prednisone 10mg (or equivalent alternative steroid).
  - Fatigue should have recovered to grade 2 or better
  - If specific toxicities are of unclear attribution (including for example: diarrhea, increased LFTs, cardiovascular disorders, mental status changes, pulmonary disorders and rash) they should be treated as possibly related to nivolumab and treated as per the tables in section 5.2.2. These toxicities must improve to grade 1 or better prior to proceeding with the second week of IL-2 therapy.
  - If toxicities have not improved to the levels listed above, nivolumab and the 2nd cycle of IL-2 should be held until toxicities improve to the above levels

- If nivolumab or IL-2 is delayed >6 weeks as a result of a toxicity, the subject must be permanently discontinued from study therapy with the following exception
  - If a steroid taper (to manage drug-related adverse events) is the reason for treatment delay >6 weeks, and the subject's adverse events recover to grade 1 or better, continuation on study could be possible if approved by the principal investigator
  
- **DURING NIVOLUMAB ONLY TIME PERIOD:**

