  - With any grade 2 or higher **non-hematologic toxicity**, hold nivolumab and refer to section 5.2.1 Events of Interest for relevant management guidelines. If adverse event is not an event of interest and improves to grade 1 or better with symptomatic management and/or supportive medications, nivolumab may be resumed in ≥ 2 weeks. If non-hematologic toxicity does not improve to grade 1 or better within 6 weeks from prior dose, nivolumab should be discontinued.

**5.2.1 IMMUNE MEDIATED EVENTS OF INTEREST (ONCE AT LEAST 1 DOSE OF NIVOLUMAB HAS BEEN ADMINISTERED) - APPLY TO NIVOLUMAB ONLY:**

Certain adverse events that are possibly immune mediated warrant special monitoring and management, and are outlined below to guide investigators.

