**5.2.1.4 Hepatic:**

Rule out non-inflammatory causes. If non-inflammatory cause, treat accordingly and continue protocol therapy. Consider imaging for obstruction.

Grade of Liver Test Elevation (NCI CTCAE v4)	Management	Follow-up
Grade 1 AST or ALT >ULN to 3x ULN and/or total bilirubin >ULN to 1.5x ULN	
 
Continue nivolumab
 
	
 
Continue liver function test monitoring per protocol
 
If worsening, treat as grade 2,3, or 4
 

Grade 2 AST or ALT >ULN to 3-5x ULN and/or total bilirubin >ULN to 1.5-3x ULN	
 
Delay nivolumab
 
Administer corticosteroids at a dose of 1-2mg/kg/day prednisone
 
	
 
Resume nivolumab and IL-2 if returns to baseline
 
If persists >5-7 days or worsens, treat as grade 3 or 4
 

Grade 3 or 4 AST or ALT >5x ULN and/or total bilirubin >3x ULN
	
 
• Discontinue nivolumab
 
• Increase frequency of monitoring to every 1-2 days
 
• 1-2mg/kg/day methylprednisolone IV or IV equivalent for grade 3 and 2 mg/kg/day methylprednisolone IV for grade 4
 
• Add prophylactic antibiotics for opportunistic infections like PCP
 
• Consult gastroenterologist
 
	
 
• If improves to grade 2, taper steroids over at least one month
 
• If does not improve within 3-5 days or worsens after improvement:             
 
○ Add mycophenolate mofetil 1g twice daily
 
○ If no response within an additional 3-5 days, consider other immunosuppressive agents per local guidelines
 
 
 

---	--	---

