#### 11.1 Study Design/Study Endpoints/Sample Size and Accrual

For the phase 1b portion of the study: We will accrue an initial cohort of 3 patients who will be treated with sequential (rather than interspersed) treatment as follows: they will receive 2 cycles of HD-IL2 given in standard fashion (two 5-day cycles one week apart) followed by nivolumab starting the week after the second IL-2 cycle and continuing every 4 weeks as per standard nivolumab dosing. If 2 or more out of 3 of the first patients suffer a grade 3 or 4 immune related toxicity of interest (see 5.2.1) **within 28 days** from the first dose of nivolumab (**DLT period**) the study will stop. The 4th patient will not be enrolled until after the analysis of the 3 patient cohort is complete and submitted to the regulatory bodies.

If <2 patients suffer a grade 3 or 4 immune related toxicity in the cohort of 3 patients, the study will enroll 7 more patients treated with Nivolumab administered intravenously at 480 mg/dose over 60 minutes every 28 days, starting 1 to 3 weeks after the start date of the first cycle of IL2. We will monitor these patients **continuously** for immune mediated dose limiting toxicities **for 28 days** from the first dose of nivolumab (**DLT period**). Up to 10 total patients will be treated and observed for toxicity for 28 days from the first dose of Nivolumab in the phase 1b portion.

If, at any time during accrual to the phase 1 b portion, 6 patients or more have a grade 3 or 4 immune mediated event of interest (as described in section 5.2.1) we will pause the study and modify/discontinue the protocol in consultation with the site principal investigators and applicable regulatory authorities. If 5 or fewer patients experience grade 3 or 4 immune mediated toxicity of interest (see 5.2.1) during the toxicity window, then the study will continue to the phase II portion.

We choose to examine toxicity after 10 patients because if 6 patients or more are found to have a DLT then the 95% exact binomial confidence interval (26% - 88%) will be > 25% and be indicative that immune mediated toxicity with this regimen is too great.

Dose-Limiting Toxicity is defined as a grade 3 or 4 immune mediated event of interest (as listed and described in section 5.2.1). Please note: immune mediated events of interest do not include those that might occur during high dose IL-2 and are reversible.

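### The Section 11.1 DLT exclusion is wider than the synopsis version and can leave reversible grade 3–4 events that end nivolumab out of the phase Ib count

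*Combined protocol and SAP*

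**What the plan says.** Three places bear on which events count.

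- **Section 11.1**, to which Section 8.8 refers for the stopping rules, states: "Dose-Limiting Toxicity is defined as a grade 3 or 4 immune mediated event of interest (as listed and described in section 5.2.1". It then qualifies this: "immune mediated events of interest do not include those that might occur during high dose IL-2 and are reversible".
- **The synopsis** carries a different qualification. There the events left out are "those that are known to occur during high dose IL-2 monotherapy and are reversible by holding IL2 dose(s) such as capillary leak syndrome".
- **Section 5.2 (Dosing delays)**, under the heading for the time after nivolumab and before the second IL-2 cycle, deals with doubtful cases: "If specific toxicities are of unclear attribution (including for example: diarrhea, increased LFTs, cardiovascular disorders, mental status changes, pulmonary disorders and rash"), then "they should be treated as possibly related to nivolumab and treated as per the tables in section 5.2.2". The only event tables in Section 5.2 are those of 5.2.1, headed "IMMUNE MEDIATED EVENTS OF INTEREST (ONCE AT LEAST 1 DOSE OF NIVOLUMAB HAS BEEN ADMINISTERED) - APPLY TO NIVOLUMAB ONLY". The grade 3–4 row of the hepatic table (5.2.1.4) begins "Discontinue nivolumab". The text above each table first asks that non-inflammatory causes be ruled out.

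Two rules use the count over 28 days from the first nivolumab dose. The study stops if 2 or more of the first 3 patients have a DLT. It pauses if 6 or more of up to 10 do, and goes on to phase II at 5 or fewer. Section 11.2 reports the DLT count and proportion as the phase Ib primary analysis and describes attribution alongside it.

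**The concern.** The 11.1 exclusion turns on whether an event *might* occur with IL-2 and whether it is reversible. It does not ask whether IL-2 caused the event, whether it began on IL-2 dosing days, or whether it settled when IL-2 was held. Section 5.2 takes the opposite presumption for doubtful events and sends them to the nivolumab tables. Section 8.4.2 makes the investigator responsible for attribution. No section says how an event of unclear attribution that was managed as possible nivolumab toxicity is classified for the DLT count.

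The phase Ib primary endpoint could therefore leave out events that were serious enough to end nivolumab. The error runs in one direction only: exclusions can lower the count and never raise it.

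**Working it through.** **1. One event under each text.** Example: nivolumab is given on day 8. A grade 3 liver-test rise appears before day 15, its cause is still unclear after work-up, and it later resolves.

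| Text | Result |
|---|---|
| Section 5.2 and hepatic table | Handled as possibly nivolumab-related; nivolumab discontinued |
| Synopsis exclusion | Not excluded unless known with IL-2 monotherapy and reversed by holding IL-2; otherwise counts |
| 11.1, read as a type of event | Could occur with IL-2 and is reversible: excluded |
| 11.1, read as timing (IL-2 dosing days) | Not on a dosing day: counts |

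The same event is or is not a DLT depending on which sentence is followed and how it is read.

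**2. Reach.** IL-2 runs on days 1–5 and 15–19 (Section 5.1.2). With nivolumab on day 8 the DLT window is about days 8–36, but the Section 5.2 rule on unclear events covers only about days 8–15. It does not reach the first 3 patients, who receive nivolumab after both cycles, nor a later patient whose nivolumab starts after cycle 2. The clash with 5.2 thus concerns at most 10 − 3 = 7 patients. The 11.1 exclusion itself is written for all 10, and so also feeds the 2-of-3 rule.

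**3. The plan's own figure.** Exact limits for x of n are the 2.5% quantile of Beta(x, n − x + 1) and the 97.5% quantile of Beta(x + 1, n − x).

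- 6 of 10: 26.2% to 87.8%, which reproduces the stated 26%–88%.
- 5 of 10: 18.7% to 81.3%.

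Six is the smallest count with a lower limit above 25%, so the threshold has no slack. If six patients are affected and one is excluded, the counted result is 5 and the study proceeds.

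**4. Chance of a pause.** Let p be the true share of patients with a grade 3–4 event of the 5.2.1 kind in the window. Let f be the share of those patients left with no countable event once the exclusion is applied. The documents give neither; both are assumed. With f acting only on the 7 interspersed patients, the count is A + B, where A ~ Bin(3, p) and B ~ Bin(7, p(1 − f)), and P(pause) = P(A + B ≥ 6).

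| True rate p | f = 0 | f = 10% | f = 25% | f = 50% |
|---|---|---|---|---|
| 25% | 2.0% | 1.4% | 0.7% | 0.2% |
| 50% | 37.7% | 29.4% | 18.6% | 6.2% |
| 60% | 63.3% | 52.5% | 36.3% | 13.9% |
| 70% | 85.0% | 75.4% | 57.6% | 25.9% |

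**5. With the 2-of-3 rule included.** The table treats the 6-of-10 rule on its own. At p = 60% the first cohort alone stops the study with probability 3 × 0.6² × 0.4 + 0.6³ = 64.8%. The chance that either rule fires is 77.9% at f = 0, 69.4% at f = 25% and 65.7% at f = 50%. Among studies that pass the first cohort (probability 1 − 0.648 = 0.352), the chance of a later pause is:

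- f = 0: (0.7791 − 0.648)/0.352 = 37%
- f = 25%: (0.6943 − 0.648)/0.352 = 13%
- f = 50%: (0.6565 − 0.648)/0.352 = 2%

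**The case against.** The best defence is that this is loose wording with a clear intent. The synopsis shows what was meant: toxicity known from IL-2 alone that goes away when IL-2 is held. The 11.1 phrase can also be read as timing. Handling an event cautiously is not the same as classifying it, and a DLT definition may differ from a management rule. Each 5.2.1 table screens out non-inflammatory causes first. Excluded drug-related events still appear in the grade 3–5 safety summary, and the monitoring committee meets monthly during phase Ib, with biweekly calls among the sites.

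Much of this stands, and it narrows the point to events still unclear after work-up. It does not remove the point. Section 11.1 is the section that governs stopping, its wording is the wider one, and neither the safety summary nor the meetings trigger the pause.

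A reader might infer more than the documents support:

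- *That reversible events in nearly every 5.2.1 organ class are exempt.* The IL-2 toxicity list in Section 1.2 does include "dyspnea, edema, oliguria and renal failure, neurotoxicity, and dermatologic complications". It names neither diarrhea nor raised liver tests; those come from the 5.2 list of unclear events. A shared organ is also not a shared event: dyspnea is not pneumonitis.
- *That the clash with 5.2 covers the whole window and all 10 patients.* Applying the loss to all 10 at p = 60% would give pause probabilities of 26% (f = 25%) and 5% (f = 50%). The 5.2 rule lasts about a week and reaches at most 7 patients.
- *That the 6-of-10 arithmetic is wrong, or that this rule is the only safeguard.* The interval is correct, and the 2-of-3 stop comes first.

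**Conclusion.** The point holds in this limited form. The 11.1 exclusion is wider than the synopsis exclusion and leaves unresolved how an unclear event handled under 5.2 as possible nivolumab toxicity is counted. Followed literally, it understates the phase Ib primary endpoint and weakens both rules that depend on it.

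That one excluded patient can turn 6 of 10 into 5 of 10 needs no assumption. The probabilities do: they assume the true rate, the excluded share and independence between patients. At a 60% rate the 6-of-10 rule alone fires with probability 63%, 36% or 14% when none, a quarter or half of the affected interspersed patients are excluded. With the 2-of-3 rule included, the chance that either fires moves less, from 78% to 69% or 66%. At a 25% rate a pause is unlikely in any case, so the wording matters most when toxicity is high, which is when the rule is needed. Under the timing reading of 11.1, or the synopsis test, fewer patients would be lost.

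**What to change.** Reconcile the synopsis note, Section 5.2 and Section 11.1:

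1. In 11.1, replace the exclusion with the narrower synopsis test.
2. In 11.1 and the synopsis, state that a grade 3–4 event in a 5.2.1 category within the 28-day window counts as a DLT if it is still of unclear attribution after non-inflammatory causes have been ruled out and is therefore handled as possibly nivolumab-related. This is narrower than counting everything managed under 5.2.1, which would let precautionary site practice decide the primary endpoint.
3. In the phase Ib report, list every excluded grade 3–4 event with the reason.
4. Correct the reference in 5.2 to tables in 5.2.2, since the tables stand in 5.2.1. Note also that 5.2.1 has no cardiovascular table, although 5.2 names cardiovascular disorders among the unclear events.

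The cost is a few sentences, a somewhat higher DLT count and a greater chance of a pause. The changes concern what is counted; no change to patient management is proposed.

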#### **Study Endpoints**

##### **Phase Ib portion:**

Primary Endpoint: To establish that the combination of High Dose Interlukin-2 and Nivolumab is safe and tolerable by monitoring 10 patients for immune mediated grade 3/4 events of interest for 28 days from the first dose of Nivolumab.

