DLT evaluable patients: All patients who receive at least 1 dose of HD IL2 and at least 1 dose of Nivolumab will be evaluable for the primary endpoint of toxicity in the phase Ib portion of the trial. Subjects who are not evaluable will be replaced.

The phase II portion of the trial will be a Simon mini-max 2-stage design. The first stage will accrue 12 patients (including any response evaluable patients accrued in the phase 1b portion). If more than 2 patients have a response (CR or PR) out of the 12 patients, then we will accrue 11 more patients for a total sample size of 23 evaluable patients. If more than 8 responses (CR or PR) are observed in the 23 evaluable patients, then we will recommend further study of the combination. This design has 80% power and 10% type I error. If the true ORR of the combined treatment is 25% or less, the probability of early termination of the trial is 39%. If the true ORR is 46% or greater, then the probability of stopping early is only 3.6%. Patients accrued in the Phase Ib portion of the trial will also be included in the Phase II if they are evaluable as defined below.

Response Evaluable Patients: All patients who receive at least 1 dose of Nivolumab and IL-2 will be evaluable for the primary endpoint of overall response proportion in the phase II portion of the trial. If response at 12 weeks is not recorded for the patient, then the patient will be considered a non-responder.

We expect accrual to the entire study to be completed over a period of 24 months.

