## **12.0 DATA AND SAFETY MONITORING**

- The Data and Safety Monitoring Committee (DSMC) of The University of Michigan Rogel Cancer Center is the DSMC for this study. This committee is responsible for monitoring the safety and data integrity of the trial. The committee will meet monthly (during the phase Ib portion) or quarterly (during the phase II portion).
- **Until the phase Ib portion is completed i.e. the first 10 patients have been treated and monitored for 28 days from the first dose of nivolumab, a biweekly phone call/webinar involving site Principal Investigators/Sub-investigator(s) from each site and relevant research staff at each site will be conducted to exchange information about toxicity/safety, subject clinical course and discern trends if any. The site investigators are highly experienced in the administration of HD IL2 and also, with nivolumab therapy.**
- At each site the study team is required to meet monthly (during the phase Ib portion) or quarterly (during the phase II portion) to discuss matters related to:
  - >Enrollment rate relative to expectations, characteristics of participants
  - >Safety of study participants (Serious Adverse Event & Adverse Event reporting)
  - >Adherence to protocol (protocol deviations)
  - >Completeness, validity and integrity of study data
  - >Retention of study participants
- These meetings are to be documented by the site data manager or study coordinator using the Protocol Specific Data and Safety Monitoring Report (DSMR), signed by the site principal investigator or co-investigator. Each site is required to submit the completed DSMR to the Multi-Site Coordinator at the University of Michigan Coordinating Center on a monthly (during

the phase Ib portion) or quarterly (during the phase II portion) basis together with other pertinent documents.

- Similarly, protocol deviations are to be documented using the Coordinating Center Deviation specified form and requires the signatures of both the sites data manager or study coordinator and the site principal investigator or co-investigator. These reports are to be sent to the University of Michigan Coordinating Center within 7 calendar days of awareness of the event and on a monthly (during the phase Ib portion) or quarterly (during the phase II portion) basis with the Protocol Specific Data and Safety Monitoring Report.

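### The DLT-evaluable definition does not require an observed 28-day window, so a patient lost from observation without a DLT fills one of the 10 places as a non-event

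*Combined protocol and SAP*

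**What the plan says.** Section 11.1 sets a DLT period of 28 days from the first nivolumab dose and defines the patients who count for it by exposure: "All patients who receive at least 1 dose of HD IL2 and at least 1 dose of Nivolumab will be evaluable" for the phase Ib toxicity endpoint. It adds that "Subjects who are not evaluable will be replaced"; Section 5.9 repeats this.

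Three places state the intended observation:
- Study Endpoints, phase Ib: "monitoring 10 patients for immune mediated grade 3/4 events of interest for 28 days from the first dose of Nivolumab".
- Section 11.1: "Up to 10 total patients will be treated and observed for toxicity for 28 days from the first dose of Nivolumab".
- Section 12.0, on when phase Ib is complete: "the first 10 patients have been treated and monitored for 28 days from the first dose of nivolumab".

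The study pauses if "6 patients or more have a grade 3 or 4 immune mediated event of interest". It goes on to phase II under the complementary condition: "If 5 or fewer patients experience grade 3 or 4 immune mediated toxicity of interest (see 5.2.1) during the toxicity window". The threshold is justified by the exact 95% interval for 6 of 10, given as 26% to 88% and so above 25%. Section 11.2 reports a plain DLT count and proportion and describes DLTs in the first 10 DLT-evaluable patients.

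**The concern.** Nothing in the evaluability definition requires the 28 days to be observed, and no passage says how to count a window cut short without a DLT. Under Sections 11.1 and 11.2 as written, such a patient is in the denominator, contributes no event and is not replaced.

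The plan handles efficacy differently. In Section 11.1 an unrecorded 12-week response counts as a non-response, which is conservative. For toxicity there is no stated rule, and the default is anti-conservative: an unseen event can lower the count but never raise it. The phase Ib primary endpoint, the 6-of-10 rule and the rule for the first three patients all depend on that count.

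**Working it through.** **Inputs from the documents.** Window 28 days; 10 patients; pause at 6 or more DLTs; reference rate 25%; for the first cohort, stop at 2 or more of 3.

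**Assumptions (not in the documents).** True DLT rate p of 50% or 60%, with 25% shown as the plan's own reference. Number of unobserved patients k = 0, 1 or 2. Leaving is unrelated to DLT risk, and leavers' events are unseen.

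**Step 1: the plan's own figure.** The exact (Clopper-Pearson) 95% limits for 6 of 10 are the 2.5% quantile of Beta(6, 5) and the 97.5% quantile of Beta(7, 4): 26.2% and 87.8%. This reproduces 26% to 88%. For 5 of 10 the limits are 18.7% and 81.3%, so 6 is the smallest count whose lower limit exceeds 25%. The arithmetic behind the threshold is right.

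**Step 2: chance of pausing.** With k patients unobserved and not replaced, all 6 DLTs must come from the other 10 − k:

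P(pause) = P(X ≥ 6), X ~ Binomial(10 − k, p).

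For p = 50%: k = 0 gives 386/1024 = 37.7%; k = 1 gives 130/512 = 25.4%; k = 2 gives 37/256 = 14.5%.

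| True DLT rate | k = 0 | k = 1 | k = 2 |
|---|---|---|---|
| 25% | 2.0% | 1.0% | 0.4% |
| 50% | 37.7% | 25.4% | 14.5% |
| 60% | 63.3% | 48.3% | 31.5% |

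The expected reported rate is p(10 − k)/10. A true 60% appears as 54% with one unobserved patient and 48% with two; a true 50% appears as 45% and 40%.

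**Step 3: some leavers' DLTs are seen before exit.** Take k = 1 and p = 60%, and suppose half of such DLTs are seen. The leaver then supplies a counted DLT with probability 0.5 × 0.6 = 0.3. The chance of exactly 5 DLTs among the other nine is 126 × 0.6⁵ × 0.4⁴ = 0.251. P(pause) = 0.483 + 0.251 × 0.3 = 0.558, or 55.8%, which lies between 48.3% and 63.3%.

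**Step 4: the first three patients.** At p = 60%, P(at least 2 of 3) = 3 × 0.36 × 0.4 + 0.216 = 64.8%. With one patient unobserved, both others must have a DLT: 0.6² = 36.0%.

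**The case against.** The strongest reply is that the plan keeps patients under observation well after treatment stops. Section 8.2 collects adverse events to 60 days after the last dose. Section 5.6 requires patients who discontinue to follow the follow-up procedures, except on withdrawal of consent for all study procedures or loss of the ability to consent freely. Section 6.2.3 has weekly toxicity calls between visits for the first 12 weeks. A reader might infer that a patient who progresses on day 5 becomes an unobserved non-event; these sections show otherwise. This part of the reply stands. It confines the gap to consent withdrawal and loss to follow-up (Section 5.8) and to death without a counted grade 3 or 4 event.

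A reader might also infer that a single dose of each drug is too little exposure for a DLT assessment. Nivolumab is given every 28 days, so one dose is essentially the planned nivolumab exposure in the window. The missing element is follow-up, not dose count.

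A third tempting step is to assume three unobserved patients. Then 5 DLTs in 7 would have an exact lower limit of 29.0%, above 25%, while the rule still said continue. Nothing in the documents supports losing 3 of 10 patients within 28 days. With one or two lost, 5 of 9 (21.2%) and 5 of 8 (24.5%) stay below 25%, so the plan's own criterion would not call for a lower threshold.

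Finally, it can be said that the plan clearly intends 28-day observation, never states that early leavers are DLT-free, and has other safeguards in the biweekly investigator calls and monthly DSMC meetings (Section 12.0). All true. But the intent is not carried into the definition that decides who is counted and who is replaced, and the calls and meetings do not correct the count.

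**Conclusion.** The point holds as a flaw in a stated rule. DLT evaluability rests on exposure alone, so a patient who leaves observation before day 28 without a DLT is kept as a non-event, contrary to the plan's own description of phase Ib. The error can run in only one direction, towards continuing.

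Its size depends on two quantities the documents do not give. If no patient leaves observation, there is no bias. At true DLT rates of 50% to 60%, one unobserved patient lowers the chance of pausing by about 12 to 15 percentage points (37.7 − 25.4 = 12.3; 63.3 − 48.3 = 15.0), and two lower it by about 23 to 32 points (37.7 − 14.5 = 23.2; 63.3 − 31.5 = 31.8). At the 25% reference rate the change is small in absolute terms. The loss is smaller if some leavers' DLTs are seen before exit, and larger if leaving is related to emerging toxicity. The 26% to 88% interval is correct and needs no change. The definition should be corrected, because it decides the phase Ib primary endpoint and entry to phase II.

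**What to change.** In Section 11.1, define a DLT-evaluable patient as one who has received at least one dose of HD IL-2 and at least one dose of nivolumab, and who either had a DLT in the 28-day window or was observed for the whole window. Replace other patients for the DLT analysis only, and keep them in the phase II response set, whose definition is unchanged. Apply the same definition to the first-three rule, and word the hold on the fourth patient so that it allows for a replacement within that cohort. In Section 11.2, add a sensitivity analysis that includes the replaced patients, counted once as non-events and once as DLTs.

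The cost is modest. One or two more patients may have to be observed before phase II opens. They count towards the 23, and 10 + 2 = 12 still fits the first stage. Keeping early leavers who had a DLT while replacing those who did not biases the DLT rate slightly upward; that is the conservative direction, and the sensitivity analysis shows its extent.
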